- Post drug (DOAC or VKA) exposure: Period starting at date of the end of drug exposure and ending at the date a new prescription of an anticoagulant or at the end of follow-up, whichever is the earliest.
- DOAC compliance: Estimated using Medication Possession Ratio (MPR) during drug exposure defined by the number of defined daily doses dispensed, divided by the number of days of drug exposure for DOAC.
- During a hospitalisation, drugs are provided by the hospital, and this time will be taken into account for calculation of drug exposure and drug discontinuation.

Outcomes

- Stroke and SE: Hospitalisation with one of the two following primary diagnoses:
 - Ischemic or undefined stroke,
 - Other systemic arterial embolism or surgical procedure for systemic arterial embolism.
- Major bleeding: Hospitalisation with one of the three following primary diagnoses:
 - Haemorrhagic stroke,
 - Other critical organ or site bleeding (intraspinal, intraocular, retroperitoneal, intraarticular or pericardial, or intramuscular),
 - Other bleeding with a transfusion during hospital stay, or resulting in death.
- Clinically relevant bleeding (CRB): Hospitalisation with one of the five following primary diagnoses:
 - Haemorrhagic stroke,
 - Other critical organ or site bleeding (intraspinal, intraocular, retroperitoneal, intraarticular or pericardial, or intramuscular),
 - Gastro-intestinal bleeding,
 - Urogenital bleeding,

- Other bleeding.
- Death: All-cause death.
- ACS: Hospitalisation with one of the two following primary diagnoses:
 - Myocardial infarction (MI),
 - Unstable angina.

Potential confounding

- Gender and age at index date,
- CHA2DS2-VASc score (stroke risk factor score) at index date: Sum of points from congestive heart failure (+1), hypertension (+1), age \geq 75 years (+2), diabetes mellitus (+1), stroke or transient ischemic attack history (+2), vascular disease history (+1), age 65-74 years (+1), female gender (+1),
- CHADS2 score (stroke risk factor score for descriptive analysis) at index date: Sum of points from congestive heart failure (+1), hypertension (+1), age \geq 75 years (+1), diabetes mellitus (+1), stroke or transient ischemic attack history (+2),
- HAS-BLED score (bleeding risk factor score) at index date: Sum of points from hypertension (+1), abnormal renal function (+1), abnormal liver function (+1), stroke history (+1), bleeding history (+1), age > 65 years (+1), drug predisposing to bleeding (+1),

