7. RATIONALE AND BACKGROUND

Atrial fibrillation (AF) is an abnormal heart rhythm characterized by irregular beating. AF is associated with a five-fold increased risk of ischemic stroke, and accounts for up to 15% of strokes in persons of all ages and 30% in those over 80 years (Wolf 1987, Camm 2010). Ischemic stroke in AF is often severe and results in long-term disability or death (Camm 2010). Vitamin K antagonists (VKA) were the reference treatment for stroke prevention in AF (SPAF) and recommended for persons at increased risk of stroke (Camm 2010, Steinberg 2014).

Xarelto[®] (rivaroxaban) is a direct oral anticoagulant (DOAC) with a different mode of action from VKA. Xarelto[®], 15 mg or 20 mg once daily, received a European market authorization for the prevention of stroke and systemic embolism in adult patients with non-valvular AF (NVAf) with one or more risk factors, such as congestive heart failure, hypertension, age \geq 75 years, diabetes mellitus, prior stroke or transient ischemic attack (EMA/CHMP/753436/2011, 22 September 2011). Two other DOAC received a European market authorization for the same indication: Pradaxa[®] (dabigatran) 110 mg or 150 mg twice daily (EMA/CHMP/ 304146/2011, 14 April 2011) and Eliquis[®] (apixaban) 2.5 mg or 5 mg twice daily (EMA/CHMP/ 608476/2012, 20 September 2012).

The market authorization of rivaroxaban is based on the ROCKET AF trial which randomized 14,264 subjects with NVAf at increased risk of stroke, to receive either rivaroxaban (at a daily dose of 20 mg) or adjusted-dose warfarin (Patel 2011). In the primary analysis, the incidence of stroke or systemic embolism was 1.71% per year in the rivaroxaban group and 2.16% per year in the warfarin group (hazard ratio, 0.79; 95%CI, 0.66 to 0.96; $p < 0.001$ for non-inferiority). Major and non-major clinically relevant bleeding incidence was 14.9% per year in the rivaroxaban group and 14.5% per year in the warfarin group (hazard ratio, 1.03; 95%CI, 0.96 to 1.11), with significant reductions in intracranial haemorrhage (0.5% vs. 0.7%, $p = 0.02$) and fatal bleeding (0.2% vs. 0.5%, $p = 0.003$) in the rivaroxaban group.

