8. RESEARCH QUESTION AND OBJECTIVES

The research question is to assess the one-year and two-year benefit-risk of rivaroxaban for SPAF compared to VKA and dabigatran among new anticoagulant users.

The main study objective is to compare the one-year and two-year risk of each of the following individual outcomes: Stroke and systemic embolism (SE), major bleeding and death between new users of anticoagulant for SPAF during drug exposure: rivaroxaban versus VKA, and rivaroxaban versus dabigatran.

Secondary objectives are:

- To describe the drug exposure to rivaroxaban, dabigatran, and VKA for SPAF in new users, as well as pattern of use;

¹ Agence Nationale de Sécurité du Médicament et des produits de santé (French Medicines Agency)

² Caisse Nationale de l'Assurance Maladie des Travailleurs Salariés (French National Health Insurance Fund for Salaried Workers)

- To compare the one-year and two-year risk of the following individual outcomes: a composite of stroke and SE, major bleeding and death, clinically relevant bleeding (CRB) and acute coronary syndrome (ACS) between new users of anticoagulant for SPAF during drug exposure: rivaroxaban versus VKA, and rivaroxaban versus dabigatran;
- To estimate the cumulative incidence and the incidence rate of each individual main and secondary outcome (stroke and SE, major bleeding, CRB, death, composite criteria, and ACS), as well as according individual diagnose of each of these outcomes, during drug exposure for rivaroxaban, dabigatran, and VKA;
- To estimate the cumulative incidence of each individual main and secondary outcome (stroke and SE, major bleeding, CRB, death, composite criteria, and ACS), as well as according individual diagnose of each of these outcomes during post-anticoagulant exposure for rivaroxaban, dabigatran, and VKA (i.e. after anticoagulant discontinuation);
- To assess outcome risk factors, including (but not limited to), gender, age, stroke and bleeding risk scores (CHA₂DS₂-VASc and HAS-BLED), low or high dosage at index date for DOAC, drug predisposing to bleeding during drug exposure and significant baseline characteristics;
- To describe and compare healthcare resources utilisation related to SPAF during rivaroxaban, dabigatran, and VKA exposure, including outcomes, and their related costs from the societal perspective and from the French healthcare insurance perspective.

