9.3.4. Outcomes

The primary outcomes are:

- **Stroke and systemic embolism (SE)** will be defined as a hospitalisation with one of the two following primary diagnoses:
 - ✓ Ischemic or undefined stroke (Giroud 2015),
 - ✓ Other systemic arterial embolism or surgical procedure for systemic arterial embolism.
- **Major bleeding**, based on International Society on Thrombosis and Haemostasis definition (Schulman 2005) and modified* to take into account the availability of information in the database, will be defined as a hospitalisation with one of the three following primary diagnoses:
 - ✓ Haemorrhagic stroke,
 - ✓ Other critical organ or site bleeding (intrapinal, intraocular, retroperitoneal, intraarticular or pericardial, or intramuscular),
 - ✓ Other bleeding with a transfusion during hospital stay, or resulting in death,

* Causes of death and haemoglobin result are not available to take into account not hospitalized fatal bleeding and bleeding causing a fall in haemoglobin level of 20g/l.
- **Clinically relevant bleeding (CRB)** will be defined as a hospitalisation with one of the five following primary diagnoses:
 - ✓ Haemorrhagic stroke,
 - ✓ Other critical organ or site bleeding (intrapinal, intraocular, retroperitoneal, intraarticular or pericardial, or intramuscular),
 - ✓ Gastro-intestinal bleeding,
 - ✓ Urogenital bleeding,
 - ✓ Other bleeding (ICD-10 codes in annex 1).
- **Death** defined as all-cause death (cause of death not available in the database).
- **Acute coronary syndrome (ACS)** will be defined as a hospitalisation with one of the two following primary diagnoses (Bezin 2015):
 - ✓ Myocardial infarction (MI),
 - ✓ Unstable angina.

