- **Outcomes:** Since deaths are recorded in the database using the national death registry, there is no information bias for this outcome. Death is a competing risk of other clinical outcomes (stroke and SE, ACS, CRB). To take into account this, the model proposed by Fine and Gray will be used to analyse clinical outcomes (Fine 1999). Clinical outcomes will be defined using the ICD-10 discharge primary diagnosis. Miscoding cannot be excluded but should be sparse for the clearly defined events studied. Nevertheless, the PMSI coding is fully independent from the study and there is no reason that a potential miscoding will be different between anticoagulant drugs, excluding an information bias. For strokes classified as undefined because CT scan or NMR were not performed, it was decided to classify undefined stroke with ischemic stroke but some could be cases of haemorrhagic stroke. A sensitivity analysis will be performed by classifying undefined stroke as haemorrhagic stroke.

Counfounding bias

The choice between a VKA and a DOAC could be related to potential confounding. To control this potential bias, the main analysis will use 1:1 matching on high dimensional propensity score (hdPS), which includes main known risk factors (gender, age, AF risk factor score, bleeding risk factor score). Indeed, one of the main limits of this database, as for many administrative databases, is the lack of information for some risk factors (e.g. smoking status, body mass index, biological results, etc.), which may or not be confounders. Without such information, it is not possible to compare the distribution of these risks factors between treatment groups, or to take it into account in the matching.

The propensity score is a statistical technique that attempts to estimate the effect of a treatment, policy, or other intervention by accounting for the covariates that predict receiving the treatment. The propensity score, and more recently hdPS (Schneeweiss 2009, Rassen 2012), were developed to summarise a large set of variables that characterize each subject for status and unmeasured confounders not recorded in a database (i.e. drugs, medical status, hospitalisation, other co-morbidities directly, or indirectly linked with unmeasured confounders). Adjusting for large numbers of covariates ascertained from subject healthcare claims data may improve control of confounding, as these variables may collectively be proxies for unobserved factors.

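### The main outcome labelled Stroke and SE leaves out haemorrhagic stroke, and no compared outcome isolates all strokes, so no all-stroke hazard ratio is planned

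*Protocol*

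**What the plan says.** The main objective (section 8) compares "Stroke and systemic embolism (SE), major bleeding and death between new users of anticoagulant for SPAF during drug exposure", each as an individual outcome, for rivaroxaban versus VKA and versus dabigatran.

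The abstract opens the definition of the first of these with "Stroke and SE: Hospitalisation with one of the two following primary diagnoses". There and in section 9.3.4 the two components are "Ischemic or undefined stroke" and systemic arterial embolism (diagnosis or surgical procedure).

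Haemorrhagic stroke sits elsewhere. The abstract's definition "Major bleeding: Hospitalisation with one of the three following primary diagnoses" lists it first, ahead of other critical-site bleeding and of other bleeding that is transfused or fatal. It is also a component of clinically relevant bleeding (CRB).

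The secondary compared outcomes (section 8) are "a composite of stroke and SE, major bleeding and death, clinically relevant bleeding (CRB) and acute coronary syndrome (ACS". The 9.7 subsection headed Outcomes plans hazard ratios for these outcomes. Results by individual diagnosis are planned as cumulative incidences and rates; the comparison bullet names no hazard ratio at that level.

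On undefined strokes, section 9.9 says "it was decided to classify undefined stroke with ischemic stroke but some could be cases of haemorrhagic stroke" and promises a sensitivity analysis that refiles undefined stroke as haemorrhagic. The lists of sensitivity analyses in the abstract (Data analysis) and in the 9.7 subsection headed Generalities describe a different move: unspecified bleeding is refiled as haemorrhagic stroke.

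**The concern.** The research question is the benefit-risk of anticoagulants for stroke prevention, and the first main outcome carries an unqualified stroke label. A reader of its hazard ratio will take it as the effect on stroke, although it covers only part of the strokes. The omitted part matters. Section 7 reports a difference between rivaroxaban and warfarin in intracranial haemorrhage (0.5% versus 0.7%), so the excluded strokes overlap with events on which the protocol itself says the drugs differ.

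The boundary between the outcome and major bleeding also runs through a class of events, undefined strokes, that the protocol admits it cannot assign with certainty. An all-stroke outcome would be unaffected by that assignment, but none is planned.

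**Working it through.** The plan states no figure for this point, so there is none to reproduce.

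**1. Where each stroke type is compared (sections 8 and 9.3.4)**

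| Compared outcome | Ischaemic or undefined stroke | Haemorrhagic stroke | Other events pooled in |
|---|---|---|---|
| Stroke and SE | yes | no | systemic embolism |
| Major bleeding | no | yes | other major bleeds |
| CRB | no | yes | all other hospitalised bleeds |
| Composite | yes | yes | systemic embolism, other major bleeds, all-cause death |
| Death, ACS | no | no | – |

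Only the composite contains every stroke type, and it does not isolate them.

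**2. Share of stroke and SE events outside the outcome**

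Inputs, from section 9.5 (earlier VKA study, specific population, per 100 person-years): stroke and SE 1.6 [1.1–2.1]; cerebral bleeding 0.5 [0.3–0.9]. Assumptions: cerebral bleeding stands in for haemorrhagic stroke; the 1.6 excludes it, since section 9.5 says that study used similar definitions; first-event rates add.

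- All stroke and SE: 1.6 + 0.5 = 2.1
- Share outside: 0.5 / 2.1 = 24%
- Varying the bleeding rate only: 0.3 / 1.9 = 16% to 0.9 / 2.5 = 36%
- Opposite ends of both intervals: 0.3 / (2.1 + 0.3) = 12.5% to 0.9 / (1.1 + 0.9) = 45%

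**3. Can the composite stand in?**

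With death at 3.5 and CRB at 2.6 as an upper bound for major bleeding, the summed component rates are at most 1.6 + 2.6 + 3.5 = 7.7. With major bleeding at its lower bound (haemorrhagic stroke alone, 0.5), they are 1.6 + 0.5 + 3.5 = 5.6. Stroke and SE are then 2.1 / 7.7 = 27% to 2.1 / 5.6 = 38% of the sum, ignoring overlap. Most of the composite is something else.

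**4. How far the two hazard ratios can differ**

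Approximation: all-stroke HR ≈ (1.6 × HR of the planned outcome + 0.5 × haemorrhagic HR) / 2.1. The hazard ratios below are illustrative; 0.71 is 0.5 / 0.7 from section 7.

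- 1.00 and 0.71: (1.600 + 0.355) / 2.1 = 0.93
- 0.90 and 0.50: (1.44 + 0.25) / 2.1 = 0.80
- 0.90 and 1.30: (1.44 + 0.65) / 2.1 = 1.00
- 1.10 and 0.70: (1.76 + 0.35) / 2.1 = 1.00

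In the first case the planned outcome misses a difference. In the last case pooling hides one.

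**5. Filing of undefined strokes**

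The protocol does not give their share; 10% and 30% of the events in the planned outcome are assumed. Refiling them as haemorrhagic lowers its rate to 1.6 × 0.90 = 1.44 or 1.6 × 0.70 = 1.12. The all-stroke rate stays at 2.1.

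The hazard ratio moves only if undefined strokes behave differently from the rest. With 0.71 for undefined strokes and 1.00 for the other events, the main result is 0.9 × 1.00 + 0.1 × 0.71 = 0.97, or 0.7 × 1.00 + 0.3 × 0.71 = 0.91. After refiling it is 1.00. If the ratios are equal, nothing moves.

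Refiling unspecified bleeding, as the two analysis lists have it, moves events only among the bleeding diagnoses and leaves Stroke and SE untouched. It does not test the risk that section 9.9 describes.

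**The case against.** Placing thromboembolic events on the benefit side and bleeding on the risk side is a coherent and openly stated choice for a benefit-risk study. The components are printed directly under the label. Haemorrhagic stroke is not lost from the main objective, because it is the first component of major bleeding, itself a main outcome. This stands, and the planned outcome should be kept.

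Pooling also has a price: the last example in step 4 shows a 10% ischaemic excess vanishing. This stands too. A reader might infer that every statement on stroke should come from the all-stroke outcome, but that would replace one partial view by another.

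Three further readings go beyond the documents:

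- That no compared outcome counts all strokes. The composite does; what is missing is an outcome that isolates them.
- That there is no hazard ratio for stroke prevention. One is planned for ischaemic or undefined stroke plus SE, and incidences by individual diagnosis will show haemorrhagic stroke in each treatment group.
- That the result cannot be set beside the authorisation trial. Section 7 reports "the incidence of stroke or systemic embolism was 1.71% per year in the rivaroxaban group" but does not say whether that trial's outcome included haemorrhagic stroke, so no mismatch is shown.

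Finally, the handling of undefined strokes is disclosed, and section 9.9 promises a sensitivity analysis. That answers the point only if the analysis lists are brought into line with it.

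**Conclusion.** The point holds in a limited form. The label on the first main outcome is broader than its definition, and no all-stroke hazard ratio is planned. About 24% of all stroke and SE events fall outside the outcome, with a range of 12.5% to 45% across both intervals.

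That size rests on VKA rates from one earlier study and on cerebral bleeding as a proxy. The proxy may be too wide: Annex 1 lists subdural and traumatic intracranial bleeds among the bleeding codes without saying which count as haemorrhagic stroke.

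Dependence on the filing of undefined strokes is certain for the event count but only possible for the hazard ratio. The mismatch in the sensitivity analysis wording is a plain inconsistency.

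The definition itself is a legitimate choice. The improvement is cheap and worth making because it concerns a main outcome.

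**What to change.** - Keep the planned main outcome and label it ischaemic or undefined stroke and SE throughout.
- Add any stroke (ischaemic, undefined or haemorrhagic) or SE as a secondary compared outcome in section 8, section 9.3.4 and the 9.7 subsection headed Outcomes. Use the same matched model and the same one-year and two-year horizons. Report it beside the planned outcome, not in place of it.
- State that haemorrhagic strokes then count both in this outcome and in major bleeding, so the two results overlap and must not be added together.
- Reconcile the sensitivity analysis in the abstract and in the 9.7 subsection headed Generalities (unspecified bleeding) with section 9.9 (undefined stroke).

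Cost: one derived outcome and its tables, from diagnoses that already serve as outcome components, with no new data source. The overlap with major bleeding is the real downside and takes one sentence to state.

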5. AMENDMENTS AND UPDATES

Number	Date	Section of study protocol	Amendment or update	Reason

6. MILESTONES

Milestones	Planned Date
Study protocol	Sep-Dec 2015
IDS and CNIL authorisation	Q4 2015-Q3 2016
Development of the Statistical Analysis Plan	Q2-Q3 2016
SNIIRAM data extraction	Q3-Q4 2016
Data management and statistical analysis	Q4 2016-Q1 2017
Final report	Q2 2017
Manuscript	Q3-Q4 2017

7. RATIONALE AND BACKGROUND

Atrial fibrillation (AF) is an abnormal heart rhythm characterized by irregular beating. AF is associated with a five-fold increased risk of ischemic stroke, and accounts for up to 15% of strokes in persons of all ages and 30% in those over 80 years (Wolf 1987, Camm 2010). Ischemic stroke in AF is often severe and results in long-term disability or death (Camm 2010). Vitamin K antagonists (VKA) were the reference treatment for stroke prevention in AF (SPAF) and recommended for persons at increased risk of stroke (Camm 2010, Steinberg 2014).

Xarelto[®] (rivaroxaban) is a direct oral anticoagulant (DOAC) with a different mode of action from VKA. Xarelto[®], 15 mg or 20 mg once daily, received a European market authorization for the prevention of stroke and systemic embolism in adult patients with non-valvular AF (NVAf) with one or more risk factors, such as congestive heart failure, hypertension, age \geq 75 years, diabetes mellitus, prior stroke or transient ischemic attack (EMA/CHMP/753436/2011, 22 September 2011). Two other DOAC received a European market authorization for the same indication: Pradaxa[®] (dabigatran) 110 mg or 150 mg twice daily (EMA/CHMP/ 304146/2011, 14 April 2011) and Eliquis[®] (apixaban) 2.5 mg or 5 mg twice daily (EMA/CHMP/ 608476/2012, 20 September 2012).

The market authorization of rivaroxaban is based on the ROCKET AF trial which randomized 14,264 subjects with NVAf at increased risk of stroke, to receive either rivaroxaban (at a daily dose of 20 mg) or adjusted-dose warfarin (Patel 2011). In the primary analysis, the incidence of stroke or systemic embolism was 1.71% per year in the rivaroxaban group and 2.16% per year in the warfarin group (hazard ratio, 0.79; 95%CI, 0.66 to 0.96; $p < 0.001$ for non-inferiority). Major and non-major clinically relevant bleeding incidence was 14.9% per year in the rivaroxaban group and 14.5% per year in the warfarin group (hazard ratio, 1.03; 95%CI, 0.96 to 1.11), with significant reductions in intracranial haemorrhage (0.5% vs. 0.7%, $p = 0.02$) and fatal bleeding (0.2% vs. 0.5%, $p = 0.003$) in the rivaroxaban group.

In France, Xarelto[®] and Pradaxa[®] were launched in this indication in August 2012, and Eliquis[®] in January 2014. The Transparency Committee of the *Haute Autorité de Santé* (HAS) gave a positive opinion for the reimbursement in this indication with a substantial medical benefit (SMR important) but no improvement in existing benefit (ASMR V), no expected public health impact, and a target population of 500 000 patients. As part of this procedure, the Transparency Committee requested Bayer to provide additional data documenting the therapeutic benefit of Xarelto[®] under actual conditions of use compared with the normal treatment of at-risk patients with NVAf:

- The characteristics of the treated patients, in particular age, gender, history and cardiovascular risk factors,
- The conditions of use of Xarelto[®]: reasons for starting treatment (particularly, first-line or second-line prescription, and risk factors associated with AF), any previous anticoagulant treatment and level of control thus obtained, concomitant treatments (in particular, antiplatelet agents and medicines with a risk of interaction), prescribed dosage (dose, amount administered daily and duration of prescription), frequency and reasons for any discontinuation of treatment and treatments started as a back-up,
- The impact on morbidity and mortality (events avoided and adverse effects, particularly bleeding), treatment compliance and quality of life in the medium and long term.

ANSM,¹ the French medicines agency, commissioned two studies using the French national claims and hospital database:

- The NACORA-BR study, performed by the CNAMTS,² was a cohort study with a main objective to compare the short-term risk of major bleeding for new NOAC users naive of VKA during the second half of 2012 to new users of VKA during the second half of 2011. Secondary objectives were to compare the risk of arterial events (stroke, systemic embolism), the risk of myocardial infarction (MI) over the same period in patients starting treatment within the AF indication, and the 30-day survival for patients hospitalized for major bleeding. This study concluded to no significant statistical difference between NOACs, dabigatran or rivaroxaban, and VKAs for the short-term risk of bleeding or arterial thromboembolic short-term risk during the early phase of anticoagulant therapy in NVAF patients (CNAMTS 2014, Maura 2015).
- The NACORA-Switch study, led by the ANSM, was a cohort study with the same main and secondary objectives for patients who switched from VKA to NOAC compared to matched patients who remained on VKA. The authors concluded that the short-term risk of severe bleeding, stroke and systemic embolism, myocardial infarction was not increased for patients switching from VKA to DOAC compared to those remaining on VKA (ANSM 2014).

The two study underline that they were conducted at the early phase of dabigatran and rivaroxaban marketing for SPAF with a short-term follow-up (3 months). The early period of marketing of a new drug is generally considered as a learning period during which disease severity and history, drug prescription and utilisation do not necessary reflect the use of the drug in daily practice some months later.

In order to provide additional information to answer the HAS requests, especially the impact on morbidity and mortality, with a longer follow-up than for the NACORA studies, a rivaroxaban versus VKA comparison, as well as a face to face comparison between the two DOAC (rivaroxaban versus dabigatran). Bayer committed to a cohort study to be initiated about six months after the launch of the two first DOAC for SPAF with two years of follow-up, using the French national claims and hospital database.

